8.5 SAFETY ANALYSES

All co-primary safety endpoints need to be achieved to claim overall safety success. Therefore no multiplicity adjustment is necessary for primary safety endpoints. For all key safety endpoints, the primary analysis population will be the safety analysis population.

8.5.1 Co-Primary Safety Endpoints and Testing

1. Cumulative rate of SSIs related to the optical properties of the IOL at Form 4, including IOL rotation SSIs for misalignment.
2. Rates of cumulative and persistent AEs at Form 4 via comparison to the ISO Safety and Performance Endpoint (SPE) rates as described in ISO 11979-7:2018.
3. BCVA logMAR of 0.3 or better at Form 4 for all-implanted and best-case test eyes.

[REDACTED] of the observed proportion is compared with the maximum allowable SPE rate. If the lower boundary of the confidence interval does not exceed the SPE rate, then the endpoint will meet the success criterion. For safety co-primary endpoint 1, the rate of SSIs related to the optical properties of the IOL will be analyzed separately in addition to overall analysis. A 95% Clopper-Pearson confidence interval will be provided for the rate of SSIs related to the optical properties of the IOL; however, this rate will not be compared to the ISO historical SPE rate. The total SSI rate, including both rotation-related and non-rotation-related SSIs, will be compared to the corresponding ISO SPE rate.

[REDACTED] The number of eyes (in the safety population) with event present at any time and the number of eyes in the safety population are included for cumulative events. For persistent events, the number of eyes with the event present at Form 4 and the number of eyes present at the Form 4 visit are included without imputation. Cumulative and persistent events will be provided for the study eye and fellow eye.

[REDACTED] For All-Implanted, the rate used for the analysis is the number of eyes with the required level measured at Form 4 and the number of eyes present at the Form 4 visit without imputation. For Best Case, the rate used for the comparison to the ISO SPE historical rate should be defined as the number of Best Case eyes with the required acuity level at Form 4 and the number of Best Case eyes present at Form 4. The analysis will be provided for the study eye. [REDACTED]

[REDACTED]

[REDACTED]

[REDACTED]

More generally stated, for each type of adverse event listed in ISO 11979-7:2018 Table E.2, the rate for the test eyes is not statistically greater than the SPE rate for that event. The comparison between the adverse event rate for the test eyes and the SPE rate for posterior chamber IOL for each adverse event will be performed using the exact test based on binomial distribution at $\alpha = 0.10$ (one-sided).

The null hypotheses for adverse event rates is that it is greater than SPE rate. The alternative hypothesis is that the adverse event rate is not greater than the SPE rate. Formally put as follows:

$$H_0: \pi_T > \hat{p}$$

$$H_A: \pi_T \leq \hat{p}$$

Where π_T is the adverse event rate for the test eyes and \hat{p} is the maximum SPE rate, for each adverse event listed in ISO 11979-7:2018 Table E.2.

As specified in ISO 11979-7:2018, the statistical success criterion is when H_0 is rejected. The statistical success criterion is equivalent to showing the one-sided 95% lower confidence limit of the rate is not greater than the historical control rate based on an exact binomial distribution.

[REDACTED]

[REDACTED]

[REDACTED]

[REDACTED]

The statistical success criterion is the rejection of H_0 . This is equivalent to showing the one-sided 95% upper confidence limit of the rate is not lower than the historical control rate based on an exact binomial distribution.

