## 7 PARTICIPANT DISCONTINUATION/ WITHDRAWAL

### 7.1 PARTICIPANT DISCONTINUATION/ WITHDRAWAL FROM THE STUDY

Discontinued subjects are those who withdraw from the study after the study informed consent document is signed and before the final visit is completed. Subjects who sign the study consent document but fail to meet eligibility criteria or withdraw prior to randomization shall be considered discontinued due to screen failure.

A subject may be discontinued prior to the final study visit for any of the following reasons, including but not limited to:

- Screen failure
- Adverse event(s); note that subjects should be followed within the study until adverse event resolution or stability

- Investigator's request (medical decision to ensure patient safety)
- Voluntary withdrawal (subject's request)
- Death
- Study terminated by Sponsor
- Loss to follow-up

Prior to discontinuing a subject, every effort should be made to contact the subject to schedule a final study visit and obtain as much follow-up data as possible. Discontinued subjects should thereafter be followed outside of the study protocol according to the Investigator's normal standard of care.

The reason for participant discontinuation or withdrawal from the study will be recorded on the Exit Case Report Form (CRF).

Randomized subjects who do not receive a study IOL or who receive a study IOL and are discontinued or withdraw from the study afterwards will not be replaced.

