6.2 STUDY POPULATION

The subject population will consist of subjects with a diagnosis of cataract with pre-existing corneal astigmatism, eligible for phacoemulsification surgery followed by IOL implantation. Eligibility for the study will be determined at the preoperative visit. If the subject gives informed consent, the subject is enrolled.

Subjects will be enrolled at up to 10 investigational sites. Investigators will be encouraged to perform cataract surgery/IOL implant for at least 20 subjects per site; no Investigator may implant more than 25% of the total number of subjects planned. Site enrollment will be closely monitored to facilitate achievement of the stated enrollment goals and an even distribution across all sites.

To allow for approximately [REDACTED] and attrition between enrolment and randomization, a total of 300 subjects will be enrolled to ensure 230 subjects, 115 test and 115 control, will be implanted. It is anticipated that 13% of the 230 subjects will not complete the study, resulting in 200 with data at the Form 4 visit.

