8 DATA ANALYSIS METHODS

8.1 DATA AND ANALYSIS CONVENTIONS

The following are some basic stipulations that, unless otherwise stated, apply by default throughout the plan.

- For the co-primary endpoints, the six-month postoperative visit (Form 4) will be the primary analysis time point unless otherwise noted. For the primary safety endpoints, the Form 4 visit will be the primary analysis time point.
- Monocular safety and effectiveness analyses will compare the test group and the control group.

- For all visual acuity-related endpoints in the study, best corrected distance visual acuity (BCDVA) and uncorrected distance visual acuity (UCDVA) are measured at 4 m using a ETDRS chart under photopic conditions. All postoperatively measured visual acuities are recorded and analyzed in logMAR for all endpoint analyses, summary statistics and calculations, and may be converted to Snellen equivalent values for tables, listings, and graphs.
- Safety data will not be imputed, although incomplete or missing dates may be imputed.
- Partial dates will be imputed for safety and effectiveness data, using the most conservative approach available; for safety data, dates will be imputed to result in the longest possible duration of a given adverse event; for effectiveness data, dates will be imputed to maximize the number of study days from the operative date.
- Partial dates in other contexts (e.g., medical history) will be imputed in a way to allow reasonable interpretation, such as to replace the missing date or the missing month with “1.” For example, a partial date recorded as “(missing date)/(missing month)/2020” will be imputed as “1/1/2020” and will be noted as “imputed” on any line listing.
- The expression “summary statistics” indicates sample size (N), mean, standard deviation (SD), median, minimum (Min), and maximum (Max) as applied to continuous variables, and indicates sample size (N), frequency and percent of relevant total as applied to categorical and some ordinal variables.
- All co-primary effectiveness and safety endpoints have to be met to claim overall effectiveness and safety success. Additional analyses and supportive analyses should not be used for the purpose of claims. Under this plan, type 1 error rates will be controlled at a significance level of 0.05 per individual hypothesis without adjustment for multiplicity.
- Data will be pooled across sites for overall analyses unless contraindicated by the poolability analysis in Section 7.8.1.

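### The SAP defines persistent adverse events in two ways for a co-primary safety endpoint; the version used for the rate, like the acuity rate, leaves out eyes that exit before Form 4 with an unresolved problem

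*SAP*

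**What the plan says.** **Counting rule.** For persistent events, SAP 8.5.1 uses "the number of eyes with the event present at Form 4 and the number of eyes present at the Form 4 visit", without imputation. For acuity in the All-implanted population it uses "the number of eyes with the required level measured at Form 4 and the number of eyes present at the Form 4 visit", also without imputation. Best Case acuity has the same Form 4 restriction. SAP 8.1 adds: "Safety data will not be imputed, although incomplete or missing dates may be imputed".

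**Cumulative events.** The same section counts these differently: "The number of eyes (in the safety population) with event present at any time and the number of eyes in the safety population". Early exits are therefore kept.

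**Population.** SAP 8.5 states: "For all key safety endpoints, the primary analysis population will be the safety analysis population".

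**Other definitions of persistent.** SAP 8.5.3 (general counting methods) defines a persistent event as one present when the study concludes, which it equates with database lock, and links it to the SPE comparison. Protocol 8.7.2.2 also refers to the conclusion of the investigation. Protocol 8.7.7 says that iritis or stromal edema found at the final visit counts as a persistent SPE event. None of the three makes Form 4 attendance a condition.

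**Exit.** Protocol 7.1 lists adverse events among the reasons to leave before the final visit, with the remark "note that subjects should be followed within the study until adverse event resolution or stability". Protocol 8.7.5 has similar wording for events ongoing at exit.

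**Expected loss.** SAP 6.2: "It is anticipated that 13% of the 230 subjects will not complete the study, resulting in 200 with data at the Form 4 visit".

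**The concern.** Take an eye that leaves at day 90 with stable stromal edema, iritis or raised IOP still under treatment. Form 4 opens at day 120, and SAP 7.2 lets an unscheduled visit stand in only if it falls inside the window. Under SAP 8.5.1 this eye is in neither numerator nor denominator. Under SAP 8.5.3 and protocol 8.7.2.2 it could be counted as persistent, and protocol 8.7.7 can be read the same way for iritis and edema. A co-primary safety result would then depend on which section the programmer follows.

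Under the 8.5.1 version, the reason for leaving may be the very outcome being measured. These three categories are not on the cumulative list in protocol 8.7.2.1, so no other SPE row picks them up. Poor acuity in an early-exit eye is likewise absent from co-primary safety endpoint 3 and appears only in a listing (SAP 8.2). The co-primary effectiveness endpoints, by contrast, have multiple imputation and an analysis that starts by treating all missing binary outcomes as failures (SAP 8.4.3). No counterpart for these safety endpoints is visible in the unredacted text.

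**Working it through.** **1. The plan's own figure.** SAP 6.2 gives 230 subjects, 115 per arm, and 13% loss. 230 × (1 − 0.13) = 200.1, which reproduces the stated 200. Per arm, 115 × 0.87 = 100.05, so about 100 test eyes reach Form 4 and about 15 do not. Equal loss by arm is an assumption.

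**2. Who is counted when an eye exits early with an unresolved problem**

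| Outcome | Cumulative row | Persistent row or acuity rate, SAP 8.5.1 | Persistent by SAP 8.5.3 / protocol 8.7.2.2 |
|---|---|---|---|
| Stromal edema, iritis, treated raised IOP | not listed | omitted | can be counted |
| CME | counted | omitted | can be counted |
| SSI, retinal detachment and the other cumulative events | counted | not listed | not listed |
| BCDVA worse than 0.3 logMAR | not listed | omitted | not applicable |

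**3. Passing counts.** An event passes if its exact lower limit does not exceed the SPE rate. For x events in n eyes the limit is the α quantile of Beta(x, n − x + 1). SAP 8.5.1 states both a one-sided α of 0.10 and a one-sided 95% limit, so both are shown for n = 100.

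| Events | Lower limit, α = 0.05 | Lower limit, α = 0.10 |
|---|---|---|
| 1 | 0.051% | 0.105% |
| 2 | 0.357% | 0.533% |
| 3 | 0.823% | 1.107% |
| 4 | 1.378% | 1.756% |

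The SPE rates are assumptions. At 0.3%, 0.5% and 1.0% the largest passing counts in 100 eyes are 1, 2 and 3 at α = 0.05, and 1, 1 and 2 at α = 0.10. In 115 eyes they are 1, 2 and 3 at either α.

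**4. How many omitted events would matter.** If the Form 4 count is already at its limit, the number of unresolved events among the 15 exits that turns a pass into a fail over all 115 eyes is the 115-eye limit + 1 − the 100-eye limit. At α = 0.05 this is 1 for each of the three rates. At α = 0.10 it is 1, 2 and 2. Starting from no events at Form 4, a fail needs 2, 3 or 4 events among the exits.

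**5. Chance of passing.** Assume an SPE rate of 1%, a true rate of 1% in completers and α = 0.05. On Form 4 attenders alone, P(X ≤ 3) with X ~ Bin(100, 0.01) is 98.2%, whatever happens in the exits. Over all 115 eyes, P(X + Y ≤ 3) with Y ~ Bin(15, r) is 97.1%, 90.2%, 76.1% and 41.7% for r = 1%, 5%, 10% and 20%. At α = 0.10 the Form 4-only figure is 92.1% (limit 2 events), while the all-eyes figures are unchanged because the 115-eye limit is still 3.

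**6. Acuity.** The closing sentence of SAP 8.5.1, whose context is redacted, is read here as the acuity rule: pass if the upper exact limit is not below the reference rate. For an assumed reference of 95% at α = 0.05, 91 of 100 just passes (upper limit 95.22%). If 2 of the 15 exits fail and 13 succeed, the result is 104 of 115, with an upper limit of 94.54%, a fail. Over assumed references of 90% to 99% and both α values, 1 to 3 failing exits turn a borderline pass into a fail.

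**The case against.** **Stronger readings the documents do not support.** A reader might infer that unresolved events in early-exit eyes vanish from the co-primary safety result. They do not: all seven cumulative categories, CME and SSI among them, are counted at any time over the whole Safety population, and CME is lost from its persistent row only. A reader might also infer that the rule always favours the lens. It does not: the 13% covers every reason for leaving, and dropping event-free exits shrinks the denominator and makes the test stricter. With 3 events, α = 0.10 and an assumed SPE rate of 1%, the lower limit is 1.107% in 100 eyes (fail) but 0.962% in 115 (pass).

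**Mitigations.** Protocol 7.1 permits exit at stability; it does not require it, and it asks sites to seek a final visit first. Protocol 8.7.7 can be read as covering iritis and edema at an early final visit, though it can equally be read as Form 4. In-window unscheduled visits can replace missing data. SAP 8.2 lists acuity histories for discontinued subjects, SAP 8.5.2 summarises losses of 10 or more letters, and SAP 8.5.3 tabulates other adverse events. SAP section 2 says that its methods supersede the protocol's, and parts of 8.5.1 are redacted.

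**What stands.** The precedence clause cannot settle a conflict between two sections of the SAP itself. The tables and listings show the omitted eyes, but the unredacted text does not bring them into the persistent-event or acuity comparison.

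**Conclusion.** The point holds as an unreconciled definition within the SAP, together with a Form 4-only count that omits event-linked exits for three persistent categories, for the persistent CME row and for acuity. Up to about 15 of 115 test eyes are affected, assuming equal loss by arm.

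Neither the net size nor the direction can be fixed from the documents, because the share leaving for adverse events is not given and the SPE rates and acuity references are assumed. One or two omitted events could change a persistent-event conclusion that is already at the boundary. It would be wrong to infer that a single event among the exits is generally decisive. The uncertainty is avoidable, since onset, resolution status and acuity history are already collected.

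**What to change.** 1. In SAP 8.5.1 and 8.5.3, state one definition of a persistent event, consistent with protocol 8.7.2.2 and 8.7.7, that says how an eye leaving before Form 4 is treated.
2. Keep the Form 4-only ISO table if it is required. Beside it, pre-specify a sensitivity analysis over all Safety-population eyes, counting an event ongoing at the last examination before exit as persistent. Early exits with and without events must both enter the denominator. Adding only those with events would inflate the rate by construction: 3 of 100 plus one event among 15 exits would give 4/101 = 4.0% instead of 4/115 = 3.5%.
3. For BCDVA, add a sensitivity analysis over all All-implanted eyes that classifies early exits by last postoperative BCDVA and shows the visit of that measurement. BCDVA is first scheduled after surgery at Form 2, so show eyes with no postoperative value as a separate count.
4. Report whether any SPE conclusion changes. This need not become an additional success criterion.

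The cost is SAP wording and one extra line per table, from data already collected. The rates may be slightly less favourable, and an early acuity value may understate final acuity, which is why its visit should be shown.

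### SAP 8.5.1 labels a non-rejection rule as rejection of the null, and sets the adverse-event comparison with the SPE rates at two different one-sided alphas

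*SAP*

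**What the plan says.** SAP 8.5.1 describes the adverse-event comparison with the ISO 11979-7 SPE rates in several ways.

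- Interval rule: "If the lower boundary of the confidence interval does not exceed the SPE rate, then the endpoint will meet the success criterion".
- In words, for each event type: "the rate for the test eyes is not statistically greater than the SPE rate for that event".
- Test: the comparison is to be "performed using the exact test based on binomial distribution at $\alpha = 0.10$ (one-sided").
- Hypotheses: "The null hypotheses for adverse event rates is that it is greater than SPE rate". The alternative is that the rate is at or below the SPE rate.
- Success: "the statistical success criterion is when H_0 is rejected", which is then said to be the same as "showing the one-sided 95% lower confidence limit of the rate is not greater than the historical control rate".

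The section's last criterion also makes rejection of its null the success condition. It equates this with the one-sided 95% upper limit not falling below the historical rate. The hypotheses for that criterion are redacted. From its position it is probably the visual acuity endpoint.

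SAP 8.1 and 8.5 require every co-primary safety endpoint to be met. SAP section 2 gives the SAP's methods precedence over the protocol's.

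**The concern.** The hypotheses and the confidence-limit rule answer different questions. Rejecting a null of "rate above SPE" would show that the device is at or below the SPE rate. A lower limit that does not exceed the SPE rate shows only that the device is not significantly above it. The SAP presents the second as if it were the first.

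The alpha is also stated twice for one comparison: 0.10 one-sided for the exact test, and a one-sided 95% limit (0.05) for the interval said to express it. Under a non-rejection rule the larger alpha is the stricter one. If the choice stays open until after unmasking, it could decide whether an event category passes.

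At stake is the pass/fail rule of a co-primary safety endpoint, and how strongly a pass may be described.

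**Working it through.** **Inputs.** SAP 6.2 plans 115 test eyes implanted, and 200 of 230 subjects with Form 4 data, so about 100 per arm if losses are equal. SAP 8.5.1 uses the safety population for cumulative events and eyes present at Form 4 for persistent events. The SPE rates are not in the documents; values from 0.1% to 5% are assumed below. All calculations are exact binomial with Clopper-Pearson limits.

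**1. The plan's own figure.** Protocol 9.5 states 99% power for effectiveness endpoints 3 and 4, using what it calls the SPE testing method: the upper limit must include the target. Take n = 100 and endpoint 4 (true rate 91.46%, target 90%). At one-sided 0.05 the smallest count whose upper limit reaches 90% is 85, and P(X ≥ 85 | 100, 0.9146) = 98.9%. At one-sided 0.025 the power is 99.5%, and at 0.10 it is 97.7%. Endpoint 3 (true 99%, target 95%) gives about 100% at each alpha. The stated 99% is therefore reproduced closely by a non-rejection rule.

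Showing that the rate is at or above target would need the lower limit to reach it. At n = 100 and one-sided 0.05, that requires 96 successes for endpoint 4 (power 6.4%) and 99 for endpoint 3 (power 73.6%). So the SPE method that the protocol had in mind is non-rejection.

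**2. Null against limit.** Rejecting H0: rate > SPE at level α requires the upper limit to be at or below the SPE rate. With zero events the upper limit is 1 − α^(1/n).

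- n = 115: 1 − 0.05^(1/115) = 2.57%; at α = 0.10, 1.98%.
- n = 100: 2.95% and 2.28%.

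For any SPE rate below these values, an event-free arm cannot reject the null as written. The same arm passes the lower-limit sentence, because its lower limit is 0.

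**3. Alpha 0.05 against 0.10 under the non-rejection rule.** The largest passing count is the largest x with P(X ≥ x | n, SPE) not below α. The final column applies the written null literally.

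| n | Assumed SPE | Limit rule (0.05) | Exact test (0.10) | Rejecting written H0 (0.05) |
|---|---|---|---|---|
| 115 | 0.5% | 2 | 2 | impossible |
| 115 | 1% | 3 | 3 | impossible |
| 115 | 2% | 5 | 4 | impossible |
| 115 | 3% | 7 | 6 | 0 |
| 115 | 5% | 10 | 9 | 1 |
| 100 | 1% | 3 | 2 | impossible |
| 100 | 2% | 5 | 4 | impossible |
| 100 | 3% | 6 | 5 | 0 |

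Two worked cases:

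- 5/115 against an assumed 2%: the 95% lower limit is 1.73%, a pass; P(X ≥ 5) = 0.082 < 0.10, a fail.
- 3/100 against an assumed 1%: the lower limit is 0.82%, a pass; P(X ≥ 3) = 0.079 < 0.10, a fail.

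Over assumed rates of 0.1% to 5% in steps of 0.01 points, the two counts differ at 73% of rates with n = 115 and 68% with n = 100, never by more than one event. Within 0.1% to 1% at n = 115 they differ at about 45% of rates.

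**4. The last criterion.** An upper limit that does not fall below a historical rate is failure to reject a null that the true rate is at or above that rate. Calling it rejection of the null has the same fault, although the null itself cannot be seen.

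**The case against.** The strongest reply is that the intended rule can be recovered. The lower-limit rule appears twice in SAP 8.5.1 and once more in words. Protocol 9.9 compares counts with a maximum allowed number, and the 99% power fits only non-rejection. On that view the reversed null is mainly a labelling error. This stands. A reader might infer from the hypotheses that the safety endpoint cannot be met for rare events, but the rest of the plan contradicts that reading. The false equivalence remains in the text that governs the endpoint.

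Other stronger readings also go too far.

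- *SAP 8.1 as a third conflict.* It says "type 1 error rates will be controlled at a significance level of 0.05 per individual hypothesis without adjustment for multiplicity", but its list applies only where nothing else is stated, and it gives no sidedness. The conflict lies within 8.5.1.
- *One-sided 0.05 as the right alpha.* The 90% intervals with 5% boundaries in SAP 8.5.2 might suggest this, but they belong to additional endpoints. The documents do not settle the choice, and 0.05 is the more lenient bar here.
- *The acuity hypotheses are reversed.* They are redacted, so only the equivalence sentence can be criticised.
- *The pass probability at twice the SPE rate as the size of the error.* With n = 115, an assumed SPE of 2% and a true rate of 4%, P(X ≤ 5) = 69% and P(X ≤ 4) = 51%. The 69% belongs to the non-rejection rule, which the correction keeps. Only the gap of about 18 points comes from the alpha conflict.

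**Conclusion.** The point holds in two parts.

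First, SAP 8.5.1 equates rejection of H0: rate > SPE with a lower-limit rule that is really non-rejection of the opposite null. This is visible in unredacted text and depends on no assumed rate. The last criterion in the section mislabels a non-rejection condition in the same way; that it concerns acuity is inferred from position.

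Second, the "exact test based on binomial distribution at $\alpha = 0.10$ (one-sided") and the one-sided 95% limit are different rules for one comparison. The allowed count can differ by one event at some SPE rates and not at others. Because the SPE rates are not in the documents, it cannot be said which event categories are affected, or how many. The sizes rest on the assumed rates and on 115 or about 100 test eyes.

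The intended direction is clear enough to correct. The intended alpha is not. Since the rule decides a co-primary safety endpoint, both should be settled before unmasking.

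**What to change.** In SAP 8.5.1:

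1. State H0: rate ≤ SPE against HA: rate > SPE for each adverse event, with the mirror image for the last criterion.
2. Define success as H0 not rejected. Report it as not statistically greater than the SPE rate, never as rejection of a null or as proof of being at or below the SPE rate.
3. Have the sponsor choose one one-sided alpha and justify it against the standard it cites. Use that alpha for both the exact test and the confidence limit, so that the two agree at every count.
4. Before unmasking, fix the maximum allowed count per event for the actual denominators: the safety population for cumulative events and eyes present at Form 4 for persistent events. Protocol 9.9 already anticipates such counts, and the table list in SAP Appendix B is redacted, so this may be partly in hand.

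The cost is SAP wording only: no new data, visits or sample size.
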